**20c Missing Data.** We will also assess missing data patterns. The primary anticipated reason for missing data is attrition due to loss to follow-up. Based on our preliminary studies, we are accounting for as large as 20% attrition from randomization to the 12-month assessment (though we expect considerably less). The baseline characteristics of those that do not provide outcome data will be examined using logistic regression models with whether or not individuals provided outcome data as the dependent variable and baseline characteristics as independent/predictor variables. Any baseline variables that predict missing data will be included in final models to increase the plausibility of the missing at random assumption. Any missing baseline data itself will be imputed using simple imputation techniques (91). Multiple imputation is often not needed/recommended in trials (92), however, we will explore the need for multiple imputation of missing data, for example where adherence predicts missing outcome data.

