1.9 Sample size estimation

A sample size of 290 participants will provide 85% power to detect an absolute difference of 20% or more in achieving viral suppression (e.g. 45% in the EUC arm vs. 65% in the intervention arm) at 12-months follow-up. This is based on a two-sided Fisher's exact test with $\alpha = 0.05$ and allowing for 20% attrition. Pilot data showed a larger difference between arms (50% in the EUC arm vs. 75% in the intervention arm), suggesting this should be a conservative sample size estimate. For the secondary outcomes, this sample size will allow detection of an effect size of 0.37 or greater on the continuous depression scale (based on $\alpha = 0.05$, a two-sided test of difference between two independent means and the same level of attrition). The sample size will also provide 90% power to detect a 20% difference in the proportion with $\geq 90\%$ adherence as was seen in our pilot data (also Fisher's exact test, $\alpha=0.05$ and 20% attrition). This is based on our pilot data, national data (Dube et al) and other research (Ciesla et al, Safran et al).

2. Data analysis plan – Data description

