3.1 Main analysis of treatment differences

The main statistical analyses will follow the intention to treat principle as much as possible. The senior statistician will remain fully blind until an initial draft of the primary analysis report is complete and needs to be checked. The trial

statistician will be unblinded. Group difference estimates between TENDAI and EUC and associated 95% confidence intervals will be reported from models appropriate to the measurement schedules and nature of the outcome in question, i.e. depending on whether the outcome is continuous or categorical. The models that will be used are outlined in the following sections. Where the outcome variable is recorded at baseline it will generally be included in the analysis model as a covariate unless stated otherwise. The significance level for the difference between TENDAI and EUC on the primary outcome will be 5% (two-sided). This significance level will also be used for the secondary outcomes, but the reader will be alerted regarding the impact of multiple testing.

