3.1.4.5 Missing outcome data

Where there are repeated post-randomisation outcome measures, missing outcome assessments will be dealt with by fitting appropriate models to all the available data using maximum likelihood methods or quasi-likelihood methods (Generalized Linear Mixed models). Such an approach provides valid inferences under the assumption that the missing data mechanism is ignorable (or MAR), i.e. all predictors of missing data are included. We will seek baseline predictors of missing data and include them as per Section 3.1. Also as mentioned in Section 3.1, we will only consider multiple imputation (MI) if post randomisation variables are found to be predictive of missing viral load outcome data (Sullivan et al), so we will assess a few pre-specified post-randomisation variables to see if they predict missing outcome data.

Baseline variables predictive of missing viral load data at 12 months.

A binary variable coding whether any primary or secondary outcomes are missing at any time point will be prepared and used as the dependent variable in a logistic regression model. The independent variables in the logistic regression model will be trial arm, site and the baseline covariate under investigation. This will be repeated for each of the baseline variables of interest. The following baseline variables will be tested as they are thought to be likely predictors of missing viral load data at 12 months: age, relationship status, education level (recoded as a single variable), income (recoded as a single variable), baseline self-report adherence to ART, baseline viral load, baseline PHQ-9 depression, access to mobile phone. Recoding of variables is described in Appendix 1 scoring of outcome measures. Each variable will be considered to predict missing viral load data if there is a significant relationship at a 5% level.

Post-randomisation variables predictive of missing viral load data at 12 months.

This will be assessed in a similar way to that used to identify which baseline variables predict missing outcome data. We will assess whether completion of therapy (in the TENDAI arm only) and self-report ART adherence at 12 months are predictive of missing data.

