If there are post-randomisation variables that predict missing outcome data, we will impute a number of datasets equal to the percentage missing data in the primary viral load outcome (Dong and Peng) or 50 datasets (whichever is higher). As well as the relevant variables from Sections 3.1.1 and 3.1.2, the imputation model will include all baseline and post-randomisation variables we find to predict missing outcome data and the putative moderating variable sex, imputing the trial arms separately as recommended by Thomas et al when moderation analysis is planned. We will endeavour to construct the imputation models as described, but if not viable, we may need to consider a set of simpler imputation models (i.e. when imputing with interaction terms we may need to remove some other variables from the imputation model). Where MI is used, we will produce estimates from both the complete case and MI data and include both in the statistical report, with the latter being the main estimates reported in the primary publication. If there are no post-randomisation variables that predict missing outcome data, but there are baseline variables predictive of missing data, these will be included in the non-logistic primary and secondary outcome analysis models (i.e. PHQ-9, self-report adherence, log viral load).

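### Unless imputation is triggered, the primary binary outcome is analysed on complete cases without most identified predictors of dropout, and the test that triggers imputation is badly specified

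*SAP*

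**What the plan says.** **Primary model.** SAP 3.1.1 fits a logistic regression of 12-month suppression on arm and site, once without and once with baseline log viral load. If viral load is missing and the death was clearly due to AIDS or high viral load, the participant is coded not suppressed. The two sensitivity analyses in SAP 3.1.5.1 vary only that coding.

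**Baseline predictors of missingness.** Protocol 20c: "Any baseline variables that predict missing data will be included in final models to increase the plausibility of the missing at random assumption". SAP 3.1 and 3.1.4.5 narrow this. If MI is used, the predictors go into the imputation model. If it is not, "these will be included in the non-logistic primary and secondary outcome analysis models (i.e. PHQ-9, self-report adherence, log viral load". The primary outcome is not in that list.

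**Gate to MI.** SAP 3.1 considers MI only if at least 10% of outcome data are missing and a post-randomisation variable predicts missing primary or secondary data. SAP 3.1.4.5 states the second condition as predicting missing viral load. Under a heading about missing 12-month viral load, the dependent variable it defines is "A binary variable coding whether any primary or secondary outcomes are missing at any time point". The post-randomisation search is run in a similar way and asks whether "completion of therapy (in the TENDAI arm only) and self-report ART adherence at 12 months are predictive of missing data". If MI is triggered, its estimate is the main published one.

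**The concern.** The gate and the covariate rule together decide which analysis produces the headline result, in a trial planned "allowing for 20% attrition". Three features look wrong.

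- The SAP ties valid inference under missing at random to including the predictors of missingness, then leaves them out of the primary model. The log viral load model is also single-visit and uses the same 12-month viral load, yet it receives them. The SAP wording does not parse either: it refers to non-logistic primary models, but the only primary model is logistic.
- The indicator tested is not the one named, and SAP 3.1 and 3.1.4.5 state the trigger differently. Two statisticians could reach different primary analyses from the same data.
- One trigger variable is collected at the visit whose absence it should explain. The other exists in one arm only.

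At stake is a primary estimate that ignores 4- and 8-month information on who is being lost. This matters if dropout related to adherence differs between arms, which is plausible in a trial where participants know their arm and contact is unequal (six sessions plus a booster against three).

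**Working it through.** **1. The plan's own figure.** SAP 1.9: "A sample size of 290 participants will provide 85% power to detect an absolute difference of 20% or more in achieving viral suppression", for example "45% in the EUC arm vs. 65% in the intervention arm". Retained per arm: 290 × 0.80 / 2 = 116. Exact enumeration of the two-sided Fisher test at 116 per arm, 45% vs 65%, α = 0.05, gives 0.850. The stated 85% reproduces and is not in dispute. The allowance corresponds to 290 − 232 = 58 participants without a primary outcome.

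**2. Who can contribute to the gate.**

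| Participant | Therapy completion | 12-month self-report adherence |
|---|---|---|
| TENDAI, lost by 12 months | known from session records | not observed |
| EUC, lost by 12 months | not defined | not observed |
| Either arm, interviewed at 12 months without viral load | TENDAI only | observed |

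Self-report adherence at 12 months is itself a secondary outcome, so its absence sets the composite indicator to 1. Everyone dropped from that test for lack of a predictor value is therefore a missing case. In EUC, only people interviewed without a viral load (for example by telephone, protocol 18b) can make the test informative about missing viral load.

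**3. Can therapy completion trigger MI?** Assumptions: TENDAI n = 145; 85% completion, so 22 non-completers (85% is pilot attendance at five or more of six sessions, whereas the SAP defines completion as four or more); viral load missing in 15% of completers. If a share e of the others miss some other item, unrelated to completion, the composite rate is p + (1 − p)e. For example, at e = 0.15, completers have 0.15 + 0.85 × 0.15 = 0.2775. Simulated chance of p < 0.05:

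| Missing in non-completers | Viral load only | Composite, e = 15% | Composite, e = 30% |
|---|---|---|---|
| 30% | 36% | 22% | 16% |
| 40% | 72% | 48% | 34% |
| 50% | 93% | 76% | 58% |

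At 70% completion the viral-load-only figures are 53%, 88% and 99%. The trigger works in TENDAI, unreliably. The composite columns rest on the unrelatedness assumption.

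**4. Bias by arithmetic, no true effect.** Assume half the participants are poor adherers, with suppression 35% in poor and 65% in good adherers, so the true rate is 50% in both arms. TENDAI loses 15% of each group, so its complete-case rate stays 50%. With r the proportion retained, the EUC rate is (0.35 r_poor + 0.65 r_good) / (r_poor + r_good):

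| EUC loss, poor / good | EUC complete-case rate | TENDAI − EUC |
|---|---|---|
| 35% / 10% | 0.8125 / 1.55 = 0.524 | −2.4 points |
| 35% / 5% | 0.8450 / 1.60 = 0.528 | −2.8 points |
| 40% / 10% | 0.7950 / 1.50 = 0.530 | −3.0 points |
| 40% / 5% | 0.8275 / 1.55 = 0.534 | −3.4 points |

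The standard error at 116 per arm is √(2 × 0.5 × 0.5 / 116) = 0.066, so the bias is about 0.4 to 0.5 standard errors. SAP 3.1 sets the level: "The significance level for the difference between TENDAI and EUC on the primary outcome will be 5% (two-sided"). A shift of that size takes it to about 6.5% to 8%.

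**5. Bias by large-sample simulation.** Assumptions: one standardised baseline predictor with log-odds 0.5 to 1.0 per SD on the outcome; 20% missing per arm unless stated.

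| Dropout depends on the predictor | True difference | Complete-case difference |
|---|---|---|
| equally in both arms | 0.200 | 0.200 |
| equally, but 25% vs 15% missing (EUC vs TENDAI) | 0.200 | 0.186 to 0.193 |
| in EUC only | 0.200 | 0.166 to 0.180 |
| in TENDAI only | 0.200 | 0.219 to 0.234 |
| in opposite directions by arm | 0.200 | 0.151 to 0.170 |
| in one arm only, no true effect | 0 | 0.020 to 0.036 in size, either sign |

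Adding the predictor and standardising returns 0.198 to 0.201 where the truth is 0.200, and about zero under no effect.

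**The case against.** The plan has more protection than its weakest rule suggests.

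- Therapy completion can trigger MI. Imputation is then done by arm, uses the identified baseline predictors and the relevant outcome-model variables, becomes the main estimate, and is reported beside the complete-case one.
- Baseline viral load, a listed candidate predictor, is in the second primary model, and deaths clearly due to AIDS or high viral load count as failures.
- Viral load may come from hospital records, and telephone or home contact can supply adherence data without blood.
- Protocol 20c promises only to explore the need for MI.
- Leaving covariates out of the logistic model may be meant to keep a marginal odds ratio, although the SAP does not give that reason.

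All of this stands, and it rules out three stronger readings.

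**That the primary model receives none of the predictors.** Not so, given baseline viral load in the second model.

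**That the primary result will usually be complete-case.** The documents give no basis for a frequency. The trigger chances in the working run from 16% to 99%, depending on assumptions.

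**That the composite indicator drowns the viral load signal.** Take a binary predictor with 40% prevalence tested in all 290, 20% missing viral load, an odds ratio of 2.0 to 2.5, and 20% to 40% missing something else. The viral-load-only test detects it in 64% to 89% of simulated trials. The composite detects it in 21% to 54% if the predictor is unrelated to the other missingness, 66% to 84% if its odds ratio there is 1.5, and 88% to 99% if the odds ratio is the same. Missed visits make a shared predictor plausible, so the direction is not established. This calculation also describes a search across both arms, not the TENDAI-only completion test.

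What the objection does not answer is the conflict with protocol 20c, the mismatch between heading and indicator, and the near absence of a trigger in EUC. Standardisation meets the marginal-estimate argument.

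**Conclusion.** The point holds as a specification fault in the rule that selects the headline estimate. The departure from protocol 20c, the two statements of the trigger and the mismatched indicator can be read directly from the text. The weakness of 12-month self-report adherence follows from when it is collected.

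The size is conditional: about 2 to 3.5 percentage points under no effect when dropout depends on adherence, or a similar prognostic factor, differently by arm. It is about zero when the dependence is equal by arm, and 0.7 to 1.4 points when the dependence is equal but the loss rates are 25% and 15%. Predictor strength, dropout patterns and completion rates are all assumptions, not figures from the documents. The bias can go either way; in the adherence example it works against TENDAI. The stated power is unaffected.

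**What to change.** In SAP 3.1 and 3.1.4.5, before the primary analysis is run:

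- (a) For the primary outcome, define the missingness indicator as missing 12-month viral load, and state the MI trigger the same way in both sections.
- (b) Replace 12-month self-report adherence as a trigger with 4- and 8-month self-report adherence, pharmacy refill, PHQ-9 and visit attendance, in both arms. Keep therapy completion for TENDAI.
- (c) If MI is not triggered, follow protocol 20c: report the primary logistic model with the identified baseline predictors added, standardised to a marginal effect, beside the two planned models.

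Running MI by arm without a significance gate when at least 10% of viral loads are missing is an option, not a required correction.

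The cost is SAP wording and a little more programming. The variables are already scheduled in protocol 18a and SAP 1.6 and 1.8.3. SAP Table 5.1, as extracted, shows no 8-month mark for self-report adherence or pharmacy refill, so confirm that those data exist.

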3.1.4.6 Method for handling multiple comparisons

There is a single primary outcome and we do not plan to adjust for multiple comparisons for the secondary outcomes.

3.1.4.7 Method for handling non-compliance (per protocol analyses)

The analysis of the primary outcome of viral suppressions will be duplicated excluding participants who did not complete the TENDAI intervention as per section 2.3.1. There is no definition of completion for the EUC arm, therefore all EUC participants could potentially be included in this analysis. Participants who were found post randomisation to have been enrolled in error/to have been ineligible will also be excluded from this analysis.

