3. Third we will provide no-cost treatment of the intervention components to each participant in the control condition who wants it when they have completed their 12 month follow up assessment.

These three enhancements of usual care will be supported by the increasing availability more generally of antidepressants in general health care. Also, awareness of depression treatment is increasing in Zimbabwe, following the rollout of the Friendship Bench, a lay-health worker delivered stepped-care program for depression in three cities.

**Intervention Group - Stepped Care-AD.** Those randomized into stepped care-AD will receive problem solving therapy for adherence and depression (PST-AD) over 6-weekly sessions, delivered by adherence counselors. The stepped care-AD will be delivered by adherence counsellors specifically trained in the intervention, who do not provide routine care and will take place in a separate building to the EUC counselling. This is to reduce the risk of contamination between the two arms, by increasing the privacy of the stepped care-AD intervention sessions, and preventing awareness of the stepped care-AD intervention impacting the counselling the EUC participants receive. Participants will be considered to have completed the intervention after finishing 4 or more sessions. To reduce participant attrition, sessions 4, 5 and 6 may be conducted by telephone for participants who are unable to travel to the clinic (for example if participants cannot travel to the clinic because of C-19 lockdown travel restriction). The 6 TENDAI sessions are as follows:

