2.3 Completion of allocated treatment, treatment fidelity and treatment experience

2.3.1 Completion of allocated treatment and treatment fidelity

The number of therapy sessions attended by participants in the TENDAI arm will be reported using the median and interquartile range.

We define completing the TENDAI treatment as completing at least four therapy sessions. Sessions are given in a pre-specified order such that a participant can only complete the fourth session of therapy once they have completed the first, second and third sessions of therapy, in that order. There is no definition of completion of therapy in the EUC arm. We will summarise the number and proportion completing at least four therapy sessions.

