3.1.1 Analysis of primary outcome

The viral load data will be coded into a binary variable as follows: <1000 copies/mL (suppressed) or ≥1000 copies/mL (not suppressed), please also see Appendix 1. Where the viral load data are missing at 12 months and the individual has died, the data will be left missing unless it is apparent from medical or death records that the person died due to high viral load or death was clearly AIDS related, in which case we will code them as not suppressed. The odds ratio at 12 months (and associated 95% CI) for <1000 copies/mL for TENDAI vs EUC will be estimated using a logistic regression model with the 12 month measure as the dependent variable, and trial arm as the independent variable, as well as the site stratification variable. We will fit two models, the one just described excluding baseline log viral load, and another including this as an independent variable, so will present odds ratio estimates both marginal and conditional with respect to baseline viral load. Moderation of treatment effects by sex will be assessed in these two final model backgrounds as outlined in Section 3.1.3.

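### The per-protocol analysis of viral suppression removes non-completers from the TENDAI arm only, so it is a non-randomised comparison that probably favours TENDAI

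*SAP*

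**What the plan says.** SAP section 3.1.4.7 states that the primary outcome analysis "will be duplicated excluding participants who did not complete the TENDAI intervention as per section 2.3.1". Section 2.3.1 supplies the definition: "We define completing the TENDAI treatment as completing at least four therapy sessions". Protocol section 11a uses the same threshold: "Participants will be considered to have completed the intervention after finishing 4 or more sessions".

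For the control arm, section 3.1.4.7 says: "There is no definition of completion for the EUC arm, therefore all EUC participants could potentially be included in this analysis". One further exclusion is not limited to an arm: "Participants who were found post randomisation to have been enrolled in error/to have been ineligible will also be excluded from this analysis".

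The model being repeated is the logistic regression of SAP section 3.1.1 on trial arm and site: "We will fit two models, the one just described excluding baseline log viral load, and another including this as an independent variable". It contains no other predictor of session attendance and no weighting. Neither document plans a complier-average or instrumental-variable analysis, and section 3.1.4.7 gives no caution on interpretation. The analysis is supplementary. For the main analysis, SAP section 3.1 says: "The main statistical analyses will follow the intention to treat principle as much as possible".

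**The concern.** Attending four sessions happens after randomisation and is unlikely to be unrelated to the outcome. The documents themselves treat missed appointments as a marker of risk for a detectable viral load (Protocol sections 8, 9 and 15). SAP section 3.1 also notes that in earlier therapy trials completion predicted whether the primary outcome was missing. Poor attenders may therefore be less often suppressed whatever the therapy does. The rule takes them out of TENDAI and leaves their counterparts in EUC, where they cannot be identified. Adjusting for site and baseline log viral load need not remove the imbalance.

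What is at stake is the only planned answer to the question of what TENDAI does in people who receive it. Readers are likely to take the estimate that way, and it does not measure that.

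**Working it through.** **The plan's own figure.** The documents give no figure for the per-protocol analysis, so the check starts from the sample size statement (SAP section 1.9): 290 randomised, 20% attrition, 45% versus 65% suppressed, two-sided Fisher's exact test at 5%. Analysed per arm: 290/2 × 0.80 = 116. Exact enumeration gives power 0.850, matching the stated 85%.

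**Inputs for the bias.**
- 116 analysed per arm and 45% suppression in EUC, from SAP section 1.9.
- Completion share c. It is not given for this trial. The nearest figure is the pilot's 85% attending at least 5 of 6 sessions (Protocol section 6a, preliminary studies), from 32 people randomised and at a stricter threshold than four. The values 75% and 65% are assumptions.
- Gap g in suppression between completers and non-completers, unrelated to treatment. It is not given. The values 10, 20 and 30 points are assumptions.

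**Formula.** With no treatment effect, both arms have the same overall rate p = c·p_C + (1−c)·p_N, where p_C and p_N are the rates in those who do and would complete and those who do not. The per-protocol difference is p_C − p = (1−c)(p_C − p_N) = (1−c)·g.

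**Rejection rate.** Normal approximation, with n1 = 116c TENDAI completers (rounded) against 116 EUC, and δ = (1−c)·g:

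Φ((δ − 1.96·SE0)/SE1) + Φ((−δ − 1.96·SE0)/SE1), with SE0 pooled and SE1 unpooled.

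Example, c = 0.85 and g = 0.30: δ = 0.15 × 0.30 = 0.045, so rates of 0.495 (n = 99) and 0.450 (n = 116). The pooled rate is 0.471, SE0 = 0.0683 and SE1 = 0.0683. The two terms are 0.096 and 0.004, giving 10.1% after rounding.

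| Completion c | Gap g (points) | Bias (points) | Odds ratio under no effect | Rejection rate |
|---|---|---|---|---|
| any | 0 | 0 | 1.00 | 5.0% |
| 0.85 | 10 | 1.5 | 1.06 | 5.6% |
| 0.85 | 20 | 3.0 | 1.13 | 7.2% |
| 0.85 | 30 | 4.5 | 1.20 | 10.1% |
| 0.75 | 20 | 5.0 | 1.22 | 10.9% |
| 0.75 | 30 | 7.5 | 1.35 | 18.4% |
| 0.65 | 20 | 7.0 | 1.32 | 15.7% |
| 0.65 | 30 | 10.5 | 1.52 | 29.3% |

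**Sensitivity to the base rate.** Fixing completers at 60% and non-completers at 30% gives the same biases (4.5, 7.5 and 10.5 points) and rejection rates of 10.2%, 18.5% and 29.3%.

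**Sensitivity to unequal missingness.** The table applies attrition equally to completers and non-completers. If instead 40% of non-completers and 15% of completers lacked a 12-month result (assumed, with the same pattern in EUC), the non-completer share among those analysed at c = 0.85 is 0.15 × 0.60/(0.15 × 0.60 + 0.85 × 0.85) = 0.111. The 4.5 points then falls to 0.111 × 30 = 3.3.

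**An estimator that keeps both arms.** The complier-average effect is the intention-to-treat risk difference divided by the share of the TENDAI arm treated. With no effect it is 0/c = 0. With the planned 20 points and c = 0.85 it is 20/0.85 = 23.5 points.

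**The case against.** Four points on the other side have force.

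First, a reader might infer that this analysis will show a benefit when there is none. The documents do not support that. The bias is zero if completers and non-completers have the same prognosis, and neither the gap nor the completion rate is known for this trial. The direction is plausible but not established. Protocol sections 11a and 18b allow sessions 4 to 6 by telephone for those unable to travel, which weakens the link between completing sessions and attending clinic.

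Second, a reader might infer that every EUC participant is kept, or that completers are patients who take their ART. Neither is what the text says. Participants found ineligible are excluded without restriction to an arm, the EUC wording is conditional, and completion means sessions attended.

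Third, the pilot figure points to about 15% non-completion or less, where the bias is modest. The 25% and 35% scenarios are assumptions. Loss to follow-up concentrated among non-completers would shrink the bias further. Against this, the pilot was small, and higher non-completion in an effectiveness trial is possible.

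Fourth, a complier-average effect defined at four sessions has a bias of its own. Session 1 is the dedicated adherence intervention (Protocol section 11a), so one to three sessions may affect viral load. The exclusion restriction is then doubtful, and the estimate is too large if those sessions work. This stands, and it determines the definition proposed in the fix.

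None of this removes the core point: non-completion excludes people from one arm only, and nothing else in the plan corrects for it.

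**Conclusion.** The concern holds for a supplementary analysis. As written, the per-protocol comparison is not randomised, and under no effect it is expected to favour TENDAI if session attenders have a better prognosis. At the pilot's attendance the bias is small to moderate. It becomes material only if non-completion is clearly higher and the gap is large. All sizes rest on an assumed gap, and those at 25% and 35% non-completion also on an assumed completion rate.

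A reader might also conclude that the trial's main result is compromised. It is not: the primary conclusion comes from the intention-to-treat analysis, which this rule does not touch. The change is worth making because it is cheap and because this is the only non-compliance analysis planned for the primary outcome.

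**What to change.** In SAP section 3.1.4.7, make a complier-average causal effect the non-compliance analysis of viral suppression:

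- Use randomised arm as the instrument and keep all randomised participants in their arms. Any exclusion for ineligibility can be a separate sensitivity analysis in both arms.
- Adjust for site and baseline log viral load, and handle missing 12-month outcomes as in the primary analysis.
- Report a risk difference next to the intention-to-treat risk difference. The SAP currently reports only odds ratios for this outcome, so the latter must be added.
- Define treatment received mainly as at least one session. Report at least four sessions as secondary, with the caveat that earlier sessions may have an effect.

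The design suits this. Counsellors delivering EUC are not trained in the intervention, TENDAI sessions are held in a separate building, and EUC participants are offered the intervention only after their 12-month assessment (Protocol section 11a). Non-compliance should therefore be essentially one-sided.

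If the existing per-protocol analysis is retained, state that it is non-randomised and probably favours TENDAI.

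Cost: SAP wording and one short analysis, using session counts already due to be summarised under SAP section 2.3.1. The downsides are wider confidence intervals and reliance on the exclusion restriction.
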